7.5 Reporting Procedures – Notifying the Study Sponsor

The study clinician will complete a SAE Form within the following timelines:

CONFIDENTIAL

This material is the property of the NYU School of Medicine and Langone Medical Center. Do not disclose or use except as authorized in writing by the study sponsor
Interventional Template Version: 11 January 2019

- All deaths and immediately life-threatening events, whether related or unrelated, will be recorded on the SAE Form and submitted to the DSMB/study sponsor within 24 hours of site awareness. See Section 1, Key Roles for contact information.
- Other SAEs regardless of relationship will be submitted to the DSMB/study sponsor within 72 hours of site awareness.

All SAEs will be followed until satisfactory resolution or until the site investigator deems the event to be chronic or the adherence to be stable. Other supporting documentation of the event may be requested by the DCC/study sponsor and should be provided as soon as possible.

As a follow-up to the initial report, within the following 48 hours of awareness of the event, the investigator shall provide further information, as applicable, on the unanticipated event or the unanticipated problem in the form of a written narrative. This should include a copy of the completed Unanticipated Problem form, and any other diagnostic information that will assist the understanding of the event. Significant new information on ongoing unanticipated adverse effects shall be provided promptly to the study sponsor.

7.6 Study Halting Rules

Review of serious, unexpected, and related AEs by the DSMB, IRB, the sponsor(s), or the FDA or relevant local regulatory authorities may result in suspension of the study.

Examples of findings that might trigger a safety review are the number of SAEs overall, the number of occurrences of a particular type of SAE, severe AEs/reactions, or increased frequency of events.

7.7 Safety Oversight

It is the responsibility of the Principal Investigator to oversee the safety of the study at his/her site. This safety monitoring will include careful assessment and appropriate reporting of adverse events as noted above, as well as the construction and implementation of a site data and safety-monitoring plan. Medical monitoring will include a regular assessment of the number and type of serious adverse events.

Safety oversight will be under the direction of a DSMB composed of individuals with the appropriate expertise, including PA, cardiovascular disease, and statistics. The DSMB will meet at least semiannually to assess safety and efficacy data of the study. The DSMB will operate under the rules of an approved charter that will be written and reviewed at the organizational meeting of the DSMB. At this time, each data element that the DSMB needs to assess will be clearly defined. The DSMB will provide its input to NIH.

8 Clinical Monitoring

The PI will conduct continuous site monitoring at the study site. Any adverse or serious adverse events or unexpected problems will be reported to the DSMB and IRB as noted.

If a subject has an elevated score indicating moderate or severe depressive symptoms on the PROMIS Depression Short Form (raw score > 16) there will be a protocol in place to contact the

CONFIDENTIAL

This material is the property of the NYU School of Medicine and Langone Medical Center. Do not disclose or use except as authorized in writing by the study sponsor
Interventional Template Version: 11 January 2019

subject to facilitate a medical referral for potential treatment. No additional clinical monitoring plan is needed.

9 Statistical Considerations

9.1 Statistical and Analytical Plans (SAP)

Aim 1. Analysis will be performed using SAS 9.4. Surveys will be administered using the Research Electronic Data Capture (REDCap) system,⁴² a secure web-based tool licensed and supported by NYU. Standard descriptive statistics will be used to describe baseline sociodemographic and clinical characteristics. Mean scores and standard deviations as well as Cronbach's α will be calculated on questionnaires to confirm reliability of study instruments in our sample. Week 2 of the Fitbit Zip PA data will be used as baseline to assure the participant is accustomed to the device and to minimize the effect of reactivity, which can last approximately one week.⁴³ To calculate total minutes/week of PA from PAVS, the following standard calculation will be used:⁴⁴ light activity will be multiplied by 0 (light activity is not included in PA recommendations but is collected to acknowledge all attempts at PA and encourage increased intensity); moderate activity is multiplied by 1; vigorous activity is multiplied by 2 (one minute of vigorous activity being equal to two minutes of moderate activity). Paired t-tests will be used to assess changes in average PA from week 2 to three-month follow-up using PAVS and Fitbit Zip data. Using Fitabase software which allows for high resolution data, we will compare minutes of PA in three levels of intensity (light, moderate, and vigorous) as well as minutes spent in sedentary behavior. We will report the percentage of weeks each participant achieves the recommended levels of PA during the monitoring period and will assess weekly PA trends. We will compare improvements in PA by levels of protocol adoption by the HCP (e.g. 100% vs. 50% adoption). At 3 months we will compare mean minutes of moderate-to-vigorous PA between those who report achieving recommended levels of PA by the PAVS to those who do not. Paired t-tests will be used to assess changes in readiness to change number, the 6MWT, BMI, waist circumference, systolic and diastolic BP, lipids, and Framingham Heart Study Risk Score. To assess meaningful improvement in CRF, we will report the percent of participants who achieve a clinically important difference of 25 meters in the 6MWT.⁴⁵ Bivariate analyses will compare all CVD risk factors, as well as other potential confounders (e.g. age, sex, race/ethnicity, depressive symptoms, quality of life, comorbidities), between those who achieve PA recommendations and those who do not.

Preliminary effect sizes of change in PA (step counts) will be generated following the Physical Activity Change Detection (PACD) approach.^{46,47} PACD is a framework for mining longitudinal PA data to detect and describe change over time. This method provides guidelines for defining time periods, detecting outliers, data smoothing, quantifying and describing change in PA patterns. Following data collection, longitudinal trends in PA will be examined descriptively and graphically to determine the optimal parameters for these analyses (e.g. window size- weekly or monthly; comparison type- baseline reference or rolling reference). An example of a possible structure is weeklong activity windows, and a static baseline reference. This would entail comparing average weekly step counts for each individual to their baseline (week 2) step counts. Significance of observed changes will be assessed, and effect sizes will be calculated to quantify the magnitude of change (e.g., Cohen's d). Plots of change over time will include error bars to reflect the precision of estimates. Benjamini-Hochberg method⁴⁸ will be used to control family-wise error rate for multiple comparisons. Lastly, exploratory linear regression analysis will be conducted to determine if change in average weekly PA is influenced by covariates. Change in physical activity between week 2 and 3 months will be the outcome variable, and the model will include up to 5 covariates, including week 2 physical activity to account for baseline levels of

CONFIDENTIAL

This material is the property of the NYU School of Medicine and Langone Medical Center. Do not disclose or use except as authorized in writing by the study sponsor
Interventional Template Version: 11 January 2019

activity. Up to 4 additional covariates will be selected from those identified in bivariate analyses of factors related to achieving physical activity goals.

Aim 2 is to conduct a process evaluation of the intervention. Implementation data will be evaluated using the PRISM framework. All data collected monthly as outlined below will be analyzed over time to assess trends. We will collect data from the EHR on the HCP practice patterns that may inform our outcomes (e.g. # patients/week). Qualitative interview data will be analyzed using content analysis, an inductive analytic method. Cardiologist, nurse practitioner, and patient interviews will be transcribed verbatim and coded by the PI using *Atlas.ti*, a software package developed for qualitative data analysis. Preliminary analysis will include a line-by-line review that yields clusters of data that will be labeled into brief headings. Codes derived from this data will be linked to interview questions (focused on acceptability and clinical utility) and result in coding categories which will be summarized across cases. Emerging themes both within and across coding categories will be identified. Methodological rigor will be maintained through an audit trail, periodic peer debriefing and member checking that will support the credibility of the study.⁴⁹

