5.6 Total Number of Participants and Sites

This is a single site study conducted at the Preventive Cardiology Center (4F). All 59 subjects will be enrolled at this site.

Recruitment will end when approximately 59 subjects are enrolled. It is expected that approximately 59 participants will be enrolled in order to produce 47 evaluable subjects. We have anticipated approximately 20% attrition.

CONFIDENTIAL

This material is the property of the NYU School of Medicine and Langone Medical Center. Do not disclose or use except as authorized in writing by the study sponsor
Interventional Template Version: 11 January 2019

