General health-related quality of life will be measured by the common data element 36-Item Short Form Health Survey (SF-36) v-1, a reliable measure ($\alpha = .90$) of physical and mental health with strong criterion validity, which is also available in Spanish.⁷⁷⁻⁸⁰ PROMIS surveys will be scored using the REDCap auto score for accuracy.

Clinical data will be collected from the EHR including potential confounding variables: age, sex, race/ethnicity, primary diagnosis, smoking status, and comorbidities (summarized as continuous data by the Charlson Comorbidity Index).⁴⁰

Sociodemographics, collected using common data elements survey⁴¹ and clinical data from the EHR will be collected at baseline. Fitbit steps will be collected daily for 3 months.

All other data will be collected baseline and at 3 months.

In the event all data collection must be remote or the subject prefers remote data collection, the PI will use baseline data from the electronic health record. The six-minute walk test can be administered remotely via an app on the subject's mobile phone with the distance walked emailed to the PI. BMI and blood pressure taken on the day of their recent clinical visit will be used for baseline data. A measuring tape will be mailed to the participant with instructions on measurement of waist circumference using standard technique. The PI or RA can schedule a videoconference to review the technique of measuring waist circumference. The most recent total cholesterol, HDL, and triglycerides results from the EHR will be used. All other baseline data collection will remain as planned.

If at 3-months remote data collection continues for a subject, the six-minute walk test will be done remotely with the mobile app. BMI and blood pressure will be used from the most recent office visit, as close to the 3-month follow-up date as possible. The patient will measure waist circumference as directed using standard technique and reviewed via video conference. The next available lab data for total cholesterol, HDL and triglycerides will be used. All other 3-month data collection will remain as planned.

If at 3-months in-person data collection is possible, the PI will resume in-person data collection as planned and meet the subject at the preventive cardiology center for data collection.

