6.1.6 Withdrawal/Early Termination Visit

If the patient subject terminates the study early and is willing to participate, the PI will collect follow-up data if the patient subject has completed at least 2.5 months of follow-up.

7 Assessment of Safety

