9.2 Analysis Datasets

This pilot study will provide preliminary effects sizes on all patient subjects and process evaluation data.

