9.3 Sample Size

The purpose of this pilot study is to test our study protocol and obtain preliminary clinical efficacy data on patient outcomes. With a type 1 error of 5% and 80% power, a sample of 59 participants will allow us to detect a minimal clinically important difference (seen in adults with CVD) in the six-minute walk test of 25 meters.⁴⁵ (effect size =0.33) There is a potential for 20% attrition based on the PIs previous work. With a type 1 error of 5% and 80% power, this sample of 47 participants will allow us to detect an effect size of 0.41 (28 meters for the six-minute walk test, an increase of 9,710 in weekly step count, and an increase of 10% of the sample achieving recommended levels of PA) and will have 80% power to detect a small effect (R^2 of .09 to .11) associated with a predictor assuming up to 4 covariates which have a combined R^2 of .4 to .2

CONFIDENTIAL

This material is the property of the NYU School of Medicine and Langone Medical Center. Do not disclose or use except as authorized in writing by the study sponsor
Interventional Template Version: 11 January 2019

with change in average weekly PA. Given our timeline and weekly volume of patients we believe it is feasible to enroll a sample of 59 participants.

10 Source Documents and Access to Source Data/Documents

Access to study records will be limited to IRB-approved members of the study team. The investigator will permit study-related monitoring, audits, and inspections by the IRB, the sponsor, and University compliance and quality assurance groups of all study related documents (e.g. source documents, regulatory documents, data collection instruments, study data etc.). The investigator will ensure the capability for inspections of applicable study-related facilities (e.g. pharmacy, diagnostic laboratory, etc.).

Participation as an investigator in this study implies acceptance of potential inspection by government regulatory authorities and applicable University compliance and quality assurance offices.

11 Quality Assurance and Quality Control

QC procedures will be implemented beginning with the data entry system and data QC checks that will be run on the database will be generated.

Following written SOPs, the PI will verify that the clinical trial is conducted and data are generated, documented (recorded), and reported in compliance with the protocol and GCP.

12 Ethics/Protection of Human Subjects

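### The paired t-test on Fitbit steps drops anyone without a three-month value and the plan has no missing-data method, so the estimated step gain is too high if step data are lost more often when steps fall

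*Combined protocol and SAP*

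**What the plan says.** Section 9.1 takes week 2 of the Fitbit record as baseline and names the test of change: "Paired t-tests will be used to assess changes in average PA from week 2 to three-month follow-up using PAVS and Fitbit Zip data". The same section uses paired t-tests for the six-minute walk test (6MWT), BMI, waist, blood pressure, lipids and other two-visit measures. It also plans weekly PA trends and the percentage of weeks in which each participant meets recommendations.

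Still in Section 9.1, effect sizes for step counts are to come from PACD applied to the longitudinal data. Window size and reference type are chosen after data collection. The example given compares each person's weekly average with that person's own week 2.

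On data and losses:
- Section 6.1.1: "Fitbit steps will be collected daily for 3 months".
- Section 5.6: "We have anticipated approximately 20% attrition", with 59 enrolled to leave 47 evaluable.
- Section 6.1.6: follow-up data are collected from early leavers only "if the patient subject has completed at least 2.5 months of follow-up".
- Section 9.3: "With a type 1 error of 5% and 80% power, this sample of 47 participants" "will allow us to detect an effect size of 0.41", which it equates with 9,710 steps/week.
- Section 9.2: the pilot will give "preliminary effects sizes on all patient subjects".

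Section 9 names no missing-data method, no sensitivity analysis for missing values and no defined analysis set.

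**The concern.** A paired t-test needs both values, so a person with weeks of steps but no month-3 value contributes nothing to it. If people whose steps are falling stop wearing the device or leave, those who remain are a favourable selection and the mean change is too high. The exploratory regression in Section 9.1 takes the same week 2 to month 3 change as its outcome, so it loses the same people.

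Preliminary efficacy data are one of the two stated purposes of this pilot (Section 9.3). An inflated effect size would make a later trial planned from it too small. Section 9.2 refers to all patient subjects, which the named test cannot deliver once month-3 values are missing. The daily record already allows a method that uses the partial series.

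**Working it through.** **Inputs from the documents.** 59 enrolled, 47 evaluable, 20% attrition (5.6); 5% type 1 error, 80% power, effect size 0.41 at n = 47, equated with 9,710 steps/week (9.3); daily steps for three months (6.1.1).

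**Assumed, because the documents give no figure.** The share of participants without month-3 steps (20%, borrowed from 5.6), the link between falling steps and loss, and the weekly noise.

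**1. The plan's own figures.** Sidedness is not stated. Two-sided, n = ((1.960 + 0.842)/0.41)² = 46.7, so 47. Power at 47 is 80.3% by the normal formula and 78.6% by the noncentral t. Enrolment: 47/(1 − 0.20) = 58.75, so 59. Both figures reproduce, and the plan expects to lose 59 − 47 = 12 people.

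**2. Implied SD of change.** 9,710/0.41 = 23,683 steps/week.

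**3. Completers against everyone.** If 47 completers show 0.41 and 12 leavers changed by δ (in SD), the effect in all 59 is (47 × 0.41 + 12 × δ)/59.

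| Leavers' change δ | Effect in all 59 | Steps/week |
|---|---|---|
| +0.41 | 0.41 | 9,710 |
| +0.20 | 0.37 | 8,698 |
| 0 | 0.33 | 7,735 |
| −0.20 | 0.29 | 6,772 |
| −0.41 | 0.24 | 5,760 |

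**4. Simulation.** 59 people, true effect 0.41 (9,710 steps/week), linear personal trends, about 20% lost. The odds of loss depend on the last recorded change from week 2. The SD-unit run had 2,000 trials per setting. The step-unit run covered weeks 2 to 13, with weekly noise SD 10,000 (assumed) and 1,500 trials per setting.

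| Link (log-odds per SD) | Completers, SD units | All weeks, SD units | Completers, steps | All weeks, steps |
|---|---|---|---|---|
| 0 | 0.410 | 0.410 | 9,790 | 9,740 |
| 0.5 | 0.451 | 0.411 | 10,970 | 9,680 |
| 1.0 | 0.483 | 0.407 | 12,240 | 9,740 |
| 1.5 | 0.514 | 0.412 | 13,330 | 9,820 |

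At the strongest link the excess is 0.514/0.41 = 1.25, or 25%, in the first run and 13,330/9,710 = 1.37, or 37%, in the second. A further run with noise SD 10,000 gave completer means from about 9,600 (no link) to about 13,600 (strong link), and 13,600/9,710 = 1.40. The range is therefore 0% to about 40%.

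**5. Form of the model.** The all-weeks estimates above used known variances and the linear trend that generated the data, which favours them. When the gain came early and then held, with step-related loss, a model with one linear slope fell to about 9,000, that is (9,710 − 9,000)/9,710 = 7% low. A model with week as a category stayed at about 9,500 to 9,900. Its precision gain over the t-test is modest, roughly 10 to 20% in sample-size terms under the assumed noise. The linear model's larger gain (standard error 2,920 against 3,440; (3,440/2,920)² = 1.39) depends on the trend being linear.

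**6. PACD.** In the example in Section 9.1, someone who left has no value in the last window. Without a rule for incomplete series, the final contrast with week 2 rests on the same people as the t-test.

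**7. Visit outcomes.** If the 12 leavers had zero change, a 25 m completer gain on the 6MWT becomes 47/59 × 25 = 19.9 m over all 59.

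**The case against.** The strongest objection is that the step-count effect size is not assigned to the paired t-test at all. Section 9.1 gives it to PACD on longitudinal data and also plans weekly trends, so the plan as a whole does use more than two weeks per person. This stands, and bias in the PACD effect size is unresolved rather than shown. It does not remove the point: the t-test remains a stated test on a primary endpoint, and PACD has no stated rule for partial series.

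Second, loss at the visit need not mean loss of steps. Section 6.1.6 concerns data the investigator collects. Steps sync after a one-time link and are downloaded at three months (6.1.1), and low wear prompts contact (5.9.2, 5.9.3). Someone who misses the visit may still have month-3 steps. This also stands, so 20% step loss is an assumption.

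Third, no document links dropout to falling steps, so any single percentage is one scenario.

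A reader might infer that the plan prescribes a completers-only analysis, or that daily steps exist for all 59. The text supports neither. Restriction to completers follows from how the test works and from the 47 evaluable, while Section 9.2 speaks of all patient subjects. Series will be cut short for leavers and non-wearers, anyone lost before week 2 has no baseline week, and PAVS has no daily series.

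**Conclusion.** The concern holds in a conditional form. The paired t-test on steps uses only people with both values, attrition of about 20% is expected, and neither the t-test nor PACD has a missing-data rule. The resulting overstatement runs from 0% to about 40% of a true 9,710 steps/week. That range assumes about 20% loss of step data and log-odds of 0 to 1.5 per SD of change. If loss is unrelated to steps, there is no bias.

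It would go too far to say that the pilot's effect size is biased, or by how much: the documents give no outcomes for leavers and no loss rate for steps. What they do support is that a better method is available from data already to be collected. The reason to change is protection against selective loss. The gain in precision is secondary.

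**What to change.** In Section 9.1:

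1. **Main step-change analysis.** Use a likelihood-based repeated-measures model on weekly steps from week 2 to month 3, with week as a categorical factor and not a single linear slope. Include every participant with any valid week from week 2 onward. Report the model-based week 2 to month 3 change with its confidence interval and effect size. State in advance what counts as a valid week, which week or weeks stand for month 3, and the covariance structure. With 12 weeks (2 to 13), an unstructured matrix would have 12 × 13/2 = 78 parameters for 59 people, so a simpler structure is needed.
2. **Paired t-test and PACD.** Keep the t-test as a sensitivity analysis, with the number analysed. Keep PACD as a description of patterns, and state how it treats incomplete series.
3. **PAVS and visit outcomes** (6MWT, BMI, waist, blood pressure, lipids). Report the completer result with the number analysed, and a sensitivity range for leavers' change. Zero change is one such value. Label it a bound, because filling in one value adds no uncertainty.
4. **Section 9.2.** Define the analysis set so that its reference to all patient subjects matches the methods.

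The cost is SAP wording and a short extra analysis in the SAS already planned, with no new visits or data. The model assumes that values are missing at random given the recorded steps. It does not protect against loss driven by a fall that was never recorded.

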5.1 Inclusion Criteria

In order to be eligible to participate in this study, an individual must meet all of the following criteria:

Adult patients in the Center who are age 18 and above will be assessed with the PAVS as part of routine care. To enroll in the home monitoring of PA:

1. Patients must achieve < 50% of PA recommendations according to PAVS screening questions
2. Have a cellular phone with data plan or a computer to sync Fitbit data
3. Speak English or Spanish
4. Be willing to wear a Fitbit Zip for 3 months

CONFIDENTIAL

This material is the property of the NYU School of Medicine and Langone Medical Center. Do not disclose or use except as authorized in writing by the study sponsor
Interventional Template Version: 11 January 2019

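### Two secondary comparisons group participants by whether they met PA recommendations although continuous minutes are available; if about 10% achieve by PAVS, the 3-month comparison is about 5 v 42

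*Combined protocol and SAP*

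**What the plan says.** Section 9.1 turns the PAVS into a continuous score in minutes per week, weighting light activity 0, moderate 1 and vigorous 2. It also takes minutes by intensity level from Fitabase. Two analyses then use achievement of the recommendation as a grouping variable.

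- The first: "At 3 months we will compare mean minutes of moderate-to-vigorous PA between those who report achieving recommended levels of PA by the PAVS", against those who do not. The source of the MVPA minutes is not named. I read it as the Fitbit, since comparing PAVS minutes between PAVS groups would be circular.
- The second: "Bivariate analyses will compare all CVD risk factors, as well as other potential confounders", "between those who achieve PA recommendations and those who do not". No instrument or time point is given.

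Section 9.1 goes on to draw up to four covariates for an exploratory linear regression from the second set of analyses. The outcome of that regression is continuous: change in PA between week 2 and 3 months.

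Three other statements bear on the group sizes. Section 5.1: "Patients must achieve < 50% of PA recommendations according to PAVS screening questions". Section 5.6: "approximately 59 participants will be enrolled in order to produce 47 evaluable subjects". Section 9.3 lists, among the effects that 47 participants can detect, "an increase of 10% of the sample achieving recommended levels of PA".

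**The concern.** Cutting a continuous score at the full recommendation treats everyone below the line alike. Section 2.1 puts the recommendation at 150 minutes per week of moderate activity, so entry is below 75. A participant who goes from 20 to 140 minutes per week falls in the same group as one who does not change. Because nobody is an achiever by PAVS at entry, the achiever group at 3 months may be small, and a comparison resting on a handful of people is imprecise.

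Two things are at stake. The first comparison is the only planned analysis that sets PAVS at 3 months against MVPA minutes, so a null result from it would say little. The second screens covariates by a yes/no variable for a regression whose outcome is continuous.

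**Working it through.** **Inputs.** From the documents: 59 enrolled, 20% attrition, 47 evaluable, 5% type 1 error, 80% power (sections 5.6 and 9.3), and no PAVS achievers at entry (section 5.1). Assumptions: a two-sided test, a 10% achiever share at 3 months, and the shape of the distribution of minutes. The documents give none of these three, so ranges are shown for the share and the shape.

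**1. The plan's own figure.** 59 x 0.80 = 47.2, so 47. For a paired mean, n = ((1.960 + 0.842)/0.41)^2 = 46.7, so 47. The normal approximation gives power 0.803 and the noncentral t gives 0.786. The stated effect size of 0.41 therefore reproduces, but for a within-person change. It says nothing about a comparison of achievers with non-achievers.

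**2. Group sizes.** If PAVS achievers go from 0% to 10%, the count is 0.10 x 47 = 4.7, so about 5 v 42. With a true share of 10%, the central 95% range of the count is 1 to 9.

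**3. Detectable difference at 5 v 42.** Normal approximation: (1.960 + 0.842) x sqrt(1/5 + 1/42) = 2.802 x 0.473 = 1.325. The noncentral t gives 1.355.

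**4. Information kept.** This is the squared correlation between the minutes and the achiever indicator. For normal minutes it is phi(z)^2 / (p(1-p)), where z is the normal quantile at 1-p.

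- At p = 5/47: z = 1.246, phi = 0.1836, p(1-p) = 0.0951, so 0.0337/0.0951 = 0.354. The loss is about 65%.
- At p = 0.50: 0.3989^2/0.25 = 0.637. The loss is about 36%.

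For exponential minutes it is p x c^2/(1-p) with c = -ln p. At 5/47, c = 2.241 and the result is 0.598, a loss of about 40%. Lognormal minutes (log-scale SD 0.5 or 1) lose 45-46% and uniform minutes 72%. The 40-65% range thus runs from right-skewed to normal. Right skew is plausible here, because light activity scores 0 and everyone starts below half the recommendation. Across all shapes and shares tried (about 4% to 50% achieving), the smallest loss is 25%, for uniform minutes at an even split.

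**5. On the correlation scale, normal minutes.** The standardised difference d converts to a point-biserial correlation d/sqrt(d^2 + 1/(p(1-p))). At 5 v 42 that is 1.355/sqrt(1.836 + 10.519) = 0.385. Dividing by sqrt(0.354) gives an underlying correlation of about 0.65. With continuous minutes and n = 47, the Fisher z method gives tanh(2.802/sqrt(44)) = 0.40.

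| Split | Detectable d | Information kept | Detectable underlying r |
|---|---|---|---|
| 5 v 42 | 1.35 | 35% | 0.65 |
| 9 v 38 | 1.06 | 48% | 0.56 |
| 14 v 33 | 0.91 | 57% | 0.51 |
| 23 v 24 | 0.84 | 64% | 0.48 |
| none (continuous) | - | 100% | 0.40 |

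**6. Simulated power at a true correlation of 0.40, n = 47.**

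- Normal minutes: Pearson 82%, Spearman about 76%; split 36-37% at 5 v 42 and about 60% at 23 v 24.
- Exponential minutes: Pearson 77%, Spearman about 63%; split about 55% at 5 v 42 and 61% at 9 v 38.

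**The case against.** The strongest reply is that the numbers above depend on an achiever count the plan never gives. That stands. A reader might infer that the plan expects a 10% rise and so a 5 v 42 split. Section 9.3 names the 10% only as an effect that 47 participants could detect. With more achievers the comparison improves steadily, as the table shows.

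A reader might also carry the 5 v 42 split over to the bivariate analyses. The documents do not support that. Those analyses name no instrument or time point, section 9.1 also reports weekly achievement over the monitoring period, and the zero start applies to PAVS only.

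A flat statement that two thirds of the information is lost would go too far as well, since it needs normal minutes and a share near 10%.

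The cut is the guideline threshold, not one chosen from the data, and the MVPA outcome in the first comparison stays continuous. Both points are fair. They justify reporting the split, not relying on it alone.

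The proposed change has limits too. Spearman's coefficient measures rank association, so it does not show that PAVS and Fitbit agree, and the plan's sentence does not claim to test agreement. Its power advantage shrinks with skew. In a check with lognormal minutes (log-scale SD 1) related linearly to the outcome, the rank correlation had less power than the 5 v 42 t-test. The case for it is that it uses the whole range of minutes and does not depend on how many people cross the line, not that it wins under every shape. Finally, screening covariates against continuous PA brings the screen closer to the regression outcome, which makes the selection more data-driven.

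**Conclusion.** The point holds in conditional form. Both comparisons group by achievement although continuous minutes are collected. If about 10% achieve by PAVS at 3 months, the first comparison is about 5 v 42, has 80% power only for a standardised difference of about 1.35, and loses roughly 40-65% of the information as the distribution runs from right-skewed to normal. Under normality the loss is still about 36% at an even split. The split in the second comparison is unknown, and that is itself a gap in the plan. The mismatch between a binary screen and a continuous regression outcome holds whatever the count.

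The consequence is small. A reader might infer that the trial's PA results are weakened. They are not: the paired t-tests, the step-count change analysis and the regression outcome are already continuous, and the participant who moves from 20 to 140 minutes contributes fully to the paired test. Nor does the 3-month MVPA comparison feed any later step. Only the bivariate analyses do, and only into a regression already labelled exploratory. This is a desirable improvement, not a flaw in the main analyses.

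**What to change.** In section 9.1:

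1. For the 3-month comparison, report the Spearman correlation with a 95% CI between PAVS minutes per week and Fitbit MVPA minutes per week. Describe it as association, not agreement.
2. Relate the CVD risk factors and covariates to continuous 3-month PA minutes, and name the instrument and time point.
3. Keep the guideline-threshold split as a descriptive count of achievers with group means.
4. If these bivariate results still select the regression covariates, label that regression as exploratory with data-driven selection.

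The cost is an edit to the analysis text before the data are analysed. It needs no new data, visits or participants. Item 4 is a reporting caveat that comes with item 2: the screen would sit closer to the regression outcome, so that part is not wholly free.
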